### WHO TOXICITY GRADING CRITERIA

	Grade 0	Grade 1	Grade 2	Grade 3	Grade 4
ENDOCRINE					
Impotence/libido	normal	decrease in normal function	--	absence of function	--
Sterility	--	--	yes	--	--
Amenorrhoea	no	yes	--	--	--
Gynaecomastia	normal	mild	pronounced or painful	--	--
Hot flushes	none	mild or < 1/day	moderate and ≥ 1/day	frequent and interferes with normal function	--
Cushingoid	normal	mild	pronounced	--	--
Endocrine - other	--	mild	moderate	severe	life-threatening
EYE					
Conjunctivitis/keratitis	none	erythema or chemosis, no steroids or antibiotics	steroids or antibiotics required	corneal ulceration or visible opacification	--
Dry eye	normal	--	requires artificial tears	--	requires enucleation
	no change	--	--	yes	--
Glaucoma	--	mild	moderate	severe	life-threatening
Eye - other					

**APPENDIX B**  
**CONCOMITANT SYSTEMIC LUPUS ERYTHEMATOSUS**  
**MEDICATIONS**

(Sample provided in this appendix is for reference only.)

Concomitant Systemic Lupus Erythematosus Medicationsa			
	Stop date	Stable date	Medication
			Start date
DMARDS/immunosuppressantsb			
Antimalarials			
Hydroxychloroquine sulfate	3 months prior to 1 st dose	4 weeks prior to 1 st dose	4 weeks prior to 1 st dose
Chloroquine			
Methotrexate	3 months prior to 1 st dose	4 weeks prior to 1 st dose	4 weeks prior to 1 st dose
Leflunomide	3 months prior to 1 st dose	8 weeks prior to 1 st dose unless an adequate cholestyramine washout has been completed. c If cholestyramine washout is performed, the last use of leflunomide must be at least 4 weeks before the 1 st dose of study drug.	4 weeks prior to 1 st dose
Mycophenolate mofetil	3 months prior to 1 st dose	4 weeks prior to 1 st dose	4 weeks prior to 1 st dose
Azathioprine	3 months prior to 1 st dose	4 weeks prior to 1 st dose	4 weeks prior to 1 st dose
Steroids			
Prednisone or prednisolone (most likely to be used)	NA	NA	4 weeks prior to 1 st dose

a Changes in background therapies, including use of steroids, should not occur after week 44.

b Dosages of these medications should remain stable during the study. Patients will be withdrawn from the study if there is an increase in the dose of immunosuppressive agents (methotrexate, azathioprine, mycophenolate mofetil [MMF], leflunomide) above the baseline level or if any new immunosuppressive agents are introduced.

c Cholestyramine washout (per ARAVA package insert) is 8 grams administered 3 times daily for 11 days (days do not need to be consecutive). Compliance for this washout is low. DMARDS=disease-modifying antirheumatic drugs; NA=not applicable.

Excluded medicationsa	Must stop by:
iv pulse steroids (methylprednisolone)	>4 weeks prior to 1 st dose
Tacrolimus	>3 months prior to 1 st dose
Cyclosporin A therapy)	>3 months prior to 1 st dose >3 months prior to 1 st dose
Cyclophosphamide	>6 months prior to 1 st dose
Biologic agents	>6 months prior to 1 st dose
Fusion proteins (eg, atacicept, abatacept, etanercept)	
Therapeutic proteins	
Monoclonal antibodies b (eg, ocrelizumab, alemtuzumab, rituximab, epratuzumab, belimumab)	
B-cell depleting agents b (eg, rituximab, epratuzumab, belimumab)	B-cell count and ALC $\geq$ normal ranges >3 months prior to 1 st dose a
Live or live-attenuated vaccines (eg, nasal flu vaccine; measles, mumps and rubella vaccine; oral polio vaccine, etc.)	
Investigational drug for the treatment of lupus	>6 months prior to 1 st dose
Investigational drug for the treatment of a condition other than lupus	>4 weeks prior to 1 st dose

a Patients will be withdrawn from the study if there is an initiation of new immunosuppressive therapy (eg, cyclophosphamide, cyclosporin, tacrolimus) or if there is an initiation of therapy with biologics for the treatment of systemic lupus erythematosus (SLE).

b For B-cell depleting agents that are also monoclonal antibodies, the most conservative restriction applies. iv=intravenous; IVIG=intravenous immunoglobulin; ALC=absolute lymphocyte count.

**Prednisone Equivalent Conversion Sheet**

Steroid type in milligrams (mg)	Betametasone	Cortisol (Hydrocortisone)	Cortisone	Deflazacort	Dexamethasone	Methylprednisolone	Prednisolone	Triamcinolone
To convert to prednisone equivalent dose, divide steroid dose by factor in this row	0.12	4	5	1.2	0.15	0.8	1	0.8
Dose of prednisone (mg)								
80	9.6	320	400	96	12	64	80	64

**APPENDIX C**  
**SYSTEMIC LUPUS ERYTHEMATOSUS DISEASE ACTIVITY INDEX 2000**

Centre: \_\_\_\_\_ Patient: \_\_\_\_\_ Visit No: \_\_\_\_\_ Scheduled: \_\_\_\_\_ Date: \_\_\_\_\_ Investigator: \_\_\_\_\_  
 dd-mmm-yy

- ◆ Only record manifestations/items due to SLE Disease Activity
- ◆ Score manifestations occurring in **the last 4 weeks**
- ◆ TO BE USED IN CONJUNCTION WITH THE SLEDAI 2000 GLOSSARY

Physicians Global Assessment	0 None	1 Mild	2 Med	3 Severe				
Descriptor	YES		No		Not Known			
1. Seizure								
2. Psychosis								
3. Organic brain syndrome								
4. Visual disturbance								
5. Cranial nerve disorder								
6. Lupus headache								
7. CVA								
8. Vasculitis								
9. Arthritis								
10. Myositis								
11. Urinary casts								
12. Hematuria								
13. Proteinuria								
14. Pyuria								
15. Rash								
16. Alopecia								
17. Mucosal ulcers								
18. Pleurisy								
19. Pericarditis								
20. Low complement								
21. Increased DNA binding								
22. Fever								
23. Thrombocytopenia								
24. Leukopenia								
SLEDAI FLARE INDEX	YES		NO		Not Known			
25. Increase in Prednisone (mg/kg/day)	Not done	No Increase	To < 0.5g	To > 0.5				
26. Added NSAID or Plaquenil								
27. New Cytoxan, Azathioprine, Methotrexate, Hospitalization (SLE)								
28. Discoid Rash, new/worse								
29. Photosensitive Rash, new/worse								
30. Lupus Profundus, new/worse								
31. Cutaneous vasculitis, new/worse								

32. Bullous lupus, , new/worse			
33. Nasopharyngeal ulcers, new/worse			
34. Pleuritis, new/worse			
35. Pericarditis, new/worse			
36. Arthritis, new/worse			
37. Fever (SLE), new/worse			
38. CNS-SLE, new/worse, requiring double prednisone or hospitalization			
39. Vasculitis, new/worse, requiring double prednisone or hospitalization			
40. Nephritis, new/worse, requiring double prednisone or hospitalization			
41. Myositis, new/worse, requiring double prednisone or hospitalization			
42. Platelets < 60,000, new/worse, req. double prednisone or hospitalization			
43. Heme-anaemia: Hb <7% req. double prednisone or hospitalization			
44. Decrease in Hb >3% requiring double prednisone or hospitalization			

SLEDAI 2000 GLOSSARY	
Seizure	Recent onset (last 28 days). Exclude metabolic, infectious or drug cause, or seizure due to past irreversible CNS damage.
Psychosis	Altered ability to function in normal activity due to severe disturbance in the perception of reality. Include hallucinations, incoherence, marked loose associations, impoverished thought content, marked illogical thinking, bizarre, disorganized, or catatonic behaviour. Exclude uraemia and drug causes.
Organic brain syndrome	Altered mental function with impaired orientation, memory or other intellectual function, with rapid onset and fluctuating clinical features. Include clouding of consciousness with reduced capacity to focus, and inability to sustain attention to environment, plus at least two of the following: perceptual disturbance, incoherent speech, insomnia or daytime drowsiness, or increased or decreased psychomotor activity. Exclude metabolic, infectious or drug causes.
Visual disturbance	Retinal and eye changes of SLE. Include cytoid bodies, retinal haemorrhages, serous exudate or haemorrhages in the choroid, optic neuritis, Exclude hypertension, infection or drug causes.
Cranial nerve disorder	New onset of sensory or motor neuropathy involving cranial nerves. Include vertigo due to lupus.
Lupus headache	Severe persistent headache: may be migrainous, but must be non-responsive to narcotic analgesia.
CVA	New onset of cerebrovascular accident (s). Exclude arteriosclerosis or hypertensive causes.
Vasculitis	Ulceration, gangrene, tender finger nodules, periungual infarction, splinter haemorrhages, or biopsy, or angiogram proof of vasculitis.
Arthritis	More than two joints with pain and signs of inflammation, i.e., tenderness, swelling, or effusion.
Myositis	Proximal muscle aching/weakness, associated with elevated creatine phosphokinase (CK) / aldolase, or electromyogram changes or a biopsy showing myositis.
Urinary casts	Haeme-granular or red blood cell casts.
Haematuria	>5 red blood cells/high power field. Exclude stone, infection or other cause.
Proteinuria	> 0.5 g/24 hours.
Pyuria	>5 white blood cells/high power field. Exclude infection.

Rash	Ongoing inflammatory lupus rash.
Alopecia	Ongoing abnormal, patchy or diffuse loss of hair due to active lupus.
Mucosal ulcers	Ongoing oral or nasal ulcerations due to active lupus.
Pleurisy	Classic and severe pleuritic chest pain or pleural rub or effusion or new pleural thickening due to lupus.
Pericarditis	Classic and severe pericardial pain or rub or effusion, or electrocardiogram, or echo confirmation.
Low complement	Decrease in CH50, C3 or C4 below the lower limit of normal for testing laboratory.
Increased DNA binding	>25% binding by Farr assay or above normal range for testing laboratory.
Fever	>38°C. Exclude infectious cause.
Thrombocytopenia	100,000 platelets/mm^3 (or < 100 x 10^9 platelets/L)
Leukopenia	<3,000 white blood cells/mm^3. Exclude drug causes.(or < 3 x 10^9 WBC/L)

**APPENDIX D**  
**BRITISH ISLES LUPUS ASSESSMENT GROUP 2004**  
(Sample provided in this appendix is for reference only.)

**British Isles Lupus Assessment Group 2004**

Only record items due to SLE Disease Activity & assessment refers to manifestations occurring in the last 4 weeks (compared with the previous 4 weeks). ♦♦ TO BE USED WITH THE GLOSSARY ♦♦

Scoring: ND Not Done  
 1 Improving  
 2 Same  
 3 Worse  
 4 New  
 Yes/No OR Value (where indicated)  
 indicate if not due to SLE activity  
 (default is 0 = not present)

**CONSTITUTIONAL**

- 1. Pyrexia - documented > 37.5°C ( )
- 2. Weight loss - unintentional > 5% ( )
- 3. Lymphadenopathy/splenomegaly ( )
- 4. Anorexia ( )

**MUCOCUTANEOUS**

- 5. Skin eruption - severe ( )
- 6. Skin eruption - mild ( )
- 7. Angio-oedema - severe ( )
- 8. Angio-oedema - mild ( )
- 9. Mucosal ulceration - severe ( )
- 10. Mucosal ulceration - mild ( )
- 11. Panniculitis/Bullous lupus - severe ( )
- 12. Panniculitis/Bullous lupus - mild ( )
- 13. Major cutaneous vasculitis/thrombosis ( )
- 14. Digital infarcts or nodular vasculitis ( )
- 15. Alopecia - severe ( )
- 16. Alopecia - mild ( )
- 17. Peri-ungual erythema/chilblains ( )
- 18. Splinter haemorrhages ( )

**NEUROPSYCHIATRIC**

- 19. Aseptic meningitis ( )
- 20. Cerebral vasculitis ( )
- 21. Demyelinating syndrome ( )
- 22. Myelopathy ( )
- 23. Acute confusional state ( )
- 24. Psychosis ( )
- 25. Acute inflammatory demyelinating polyradiculoneuropathy ( )
- 26. Mononeuropathy (single/multiplex) ( )
- 27. Cranial neuropathy ( )
- 28. Plexopathy ( )
- 29. Polyneuropathy ( )
- 30. Seizure disorder ( )
- 31. Status epilepticus ( )
- 32. Cerebrovascular disease (not due to vasculitis) ( )
- 33. Cognitive dysfunction ( )
- 34. Movement disorder ( )
- 35. Autonomic disorder ( )
- 36. Cerebellar ataxia (isolated) ( )
- 37. Lupus headache - severe unremitting ( )
- 38. Headache from IC hypertension ( )

**MUSCULOSKELETAL**

- 39. Myositis - severe ( )
- 40. Myositis - mild ( )
- 41. Arthritis (severe) ( )
- 42. Arthritis (moderate)/Tendonitis/Tenosynovitis ( )
- 43. Arthritis (mild)/Arthralgia/Myalgia ( )

Weight (kg):	Serum urea (mmol/l):
African ancestry: Yes/No	Serum albumin (g/l):

**CARDIORESPIRATORY**

- 44. Myocarditis - mild ( )
- 45. Myocarditis/Endocarditis + Cardiac failure ( )
- 46. Arrhythmia ( )
- 47. New valvular dysfunction ( )
- 48. Pleurisy/Pericarditis ( )
- 49. Cardiac tamponade ( )
- 50. Pleural effusion with dyspnoea ( )
- 51. Pulmonary haemorrhage/vasculitis ( )
- 52. Interstitial alveolitis/pneumonitis ( )
- 53. Shrinking lung syndrome ( )
- 54. Aortitis ( )
- 55. Coronary vasculitis ( )

**GASTROINTESTINAL**

- 56. Lupus peritonitis ( )
- 57. Abdominal serositis or ascites ( )
- 58. Lupus enteritis/colitis ( )
- 59. Malabsorption ( )
- 60. Protein losing enteropathy ( )
- 61. Intestinal pseudo-obstruction ( )
- 62. Lupus hepatitis ( )
- 63. Acute lupus cholecystitis ( )
- 64. Acute lupus pancreatitis ( )

**OPHTHALMIC**

- 65. Orbital inflammation/myositis/proptosis ( )
- 66. Keratitis - severe ( )
- 67. Keratitis - mild ( )
- 68. Anterior uveitis ( )
- 69. Posterior uveitis/retinal vasculitis - severe ( )
- 70. Posterior uveitis/retinal vasculitis - mild ( )
- 71. Episcleritis ( )
- 72. Scleritis - severe ( )
- 73. Scleritis - mild ( )
- 74. Retinal/choroidal vaso-occlusive disease ( )
- 75. Isolated cotton-wool spots (cytoid bodies) ( )
- 76. Optic neuritis ( )
- 77. Anterior ischaemic optic neuropathy ( )

**RENAL**

- 78. Systolic blood pressure (mm Hg) value ( )
- 79. Diastolic blood pressure (mm Hg) value ( )
- 80. Accelerated hypertension Yes/No ( )
- 81. Urine dipstick protein (+=1, +=2, +++=3) ( )
- 82. Urine albumin-creatinine ratio mg/mmol ( )
- 83. Urine protein-creatinine ratio mg/mmol ( )
- 84. 24 hour urine protein (g) value ( )
- 85. Nephrotic syndrome Yes/No ( )
- 86. Creatinine (plasma/serum) µmol/l ( )
- 87. GFR (calculated) ml/min/1.73 m^2 ( )
- 88. Active urinary sediment Yes/No ( )
- 89. Active nephritis Yes/No ( )

**HAEMATOLOGY**

- 90. Haemoglobin (g/dl) value ( )
- 91. Total white cell count (x 10^9/l) value ( )
- 92. Neutrophils (x 10^9/l) value ( )
- 93. Lymphocytes (x 10^9/l) value ( )
- 94. Platelets (x 10^9/l) value ( )
- 95. TTP ( )
- 96. Evidence of active haemolysis Yes/No ( )
- 97. Coombs' test positive (isolated) Yes/No ( )

Revision: 12/Jan/2007

**APPENDIX E**  
**MEDICAL OUTCOME SURVEY SHORT FORM 36**

(Sample provided in this appendix is for reference only.)

## Medical Outcome Survey Short Form 36

# Your Health and Well-Being

This survey asks for your views about your health. This information will help keep track of how you feel and how well you are able to do your usual activities. *Thank you for completing this survey!*

For each of the following questions, please mark an  in the one box that best describes your answer.

1. In general, would you say your health is:

Excellent	Very good	Good	Fair	Poor
▼	▼	▼	▼	▼
				

2. Compared to one year ago, how would you rate your health in general now?

Much better now than one year ago	Somewhat better now than one year ago	About the same as one year ago	Somewhat worse now than one year ago	Much worse now than one year ago
▼	▼	▼	▼	▼
				

SF-36v2™ Health Survey © 1996, 2000 by QualityMetric Incorporated and Medical Outcomes Trust. All Rights Reserved.  
SF-36® is a registered trademark of Medical Outcomes Trust.  
(SF-36v2 Standard, US Version 2.0)

**3. The following questions are about activities you might do during a typical day. Does your health now limit you in these activities? If so, how much?**

Yes, limited a lot	Yes, limited a little	No, not limited at all
▼	▼	▼

a. Vigorous activities , such as running, lifting heavy objects, participating in strenuous sports .....			
b. Moderate activities , such as moving a table, pushing a vacuum cleaner, bowling, or playing golf .....			
c. Lifting or carrying groceries .....			
d. Climbing several flights of stairs.....			
e. Climbing one flight of stairs.....			
f. Bending, kneeling, or stooping.....			
g. Walking more than a mile .....			
h. Walking several hundred yards .....			
i. Walking one hundred yards .....			
j. Bathing or dressing yourself.....			

SF-36v2™ Health Survey © 1996, 2000 by QualityMetric Incorporated and Medical Outcomes Trust. All Rights Reserved.  
 SF-36® is a registered trademark of Medical Outcomes Trust.  
 (SF-36v2 Standard, US Version 2.0)

4. During the past 4 weeks, how much of the time have you had any of the following problems with your work or other regular daily activities as a result of your physical health?

All of the time	Most of the time	Some of the time	A little of the time	None of the time
▼	▼	▼	▼	▼

- a. Cut down on the amount of time you spent on work or other activities ..... 1 ..... 2 ..... 3 ..... 4 ..... 5
- b. Accomplished less than you would like ..... 1 ..... 2 ..... 3 ..... 4 ..... 5
- c. Were limited in the kind of work or other activities ..... 1 ..... 2 ..... 3 ..... 4 ..... 5
- d. Had difficulty performing the work or other activities (for example, it took extra effort) ..... 1 ..... 2 ..... 3 ..... 4 ..... 5

5. During the past 4 weeks, how much of the time have you had any of the following problems with your work or other regular daily activities as a result of any emotional problems (such as feeling depressed or anxious)?

All of the time	Most of the time	Some of the time	A little of the time	None of the time
▼	▼	▼	▼	▼

- a. Cut down on the amount of time you spent on work or other activities ..... 1 ..... 2 ..... 3 ..... 4 ..... 5
- b. Accomplished less than you would like ..... 1 ..... 2 ..... 3 ..... 4 ..... 5
- c. Did work or other activities less carefully than usual ..... 1 ..... 2 ..... 3 ..... 4 ..... 5

SF-36v2™ Health Survey © 1996, 2000 by QualityMetric Incorporated and Medical Outcomes Trust. All Rights Reserved.  
SF-36® is a registered trademark of Medical Outcomes Trust.  
(SF-36v2 Standard, US Version 2.0)

6. During the past 4 weeks, to what extent has your physical health or emotional problems interfered with your normal social activities with family, friends, neighbors, or groups?

Not at all	Slightly	Moderately	Quite a bit	Extremely
▼	▼	▼	▼	▼
				

7. How much bodily pain have you had during the past 4 weeks?

None	Very mild	Mild	Moderate	Severe	Very Severe
▼	▼	▼	▼	▼	▼
					

8. During the past 4 weeks, how much did pain interfere with your normal work (including both work outside the home and housework)?

Not at all	A little bit	Moderately	Quite a bit	Extremely
▼	▼	▼	▼	▼
				

SF-36v2™ Health Survey © 1996, 2000 by QualityMetric Incorporated and Medical Outcomes Trust. All Rights Reserved.  
SF-36® is a registered trademark of Medical Outcomes Trust.  
(SF-36v2 Standard, US Version 2.0)

9. These questions are about how you feel and how things have been with you during the past 4 weeks. For each question, please give the one answer that comes closest to the way you have been feeling. How much of the time during the past 4 weeks...

	All of the time	Most of the time	Some of the time	A little of the time	None of the time
	▼	▼	▼	▼	▼
a Did you feel full of life? .....	 1	 2	 3	 4	 5
b Have you been very nervous? .....	 1	 2	 3	 4	 5
c Have you felt so down in the dumps that nothing could cheer you up? .....	 1	 2	 3	 4	 5
d Have you felt calm and peaceful? .....	 1	 2	 3	 4	 5
e Did you have a lot of energy? .....	 1	 2	 3	 4	 5
f Have you felt downhearted and depressed? .....	 1	 2	 3	 4	 5
g Did you feel worn out? .....	 1	 2	 3	 4	 5
h Have you been happy? .....	 1	 2	 3	 4	 5
i Did you feel tired? .....	 1	 2	 3	 4	 5

10. During the past 4 weeks, how much of the time has your physical health or emotional problems interfered with your social activities (like visiting friends, relatives, etc.)?

All of the time	Most of the time	Some of the time	A little of the time	None of the time
▼	▼	▼	▼	▼
 1	 2	 3	 4	 5

SF-36v2™ Health Survey © 1996, 2000 by QualityMetric Incorporated and Medical Outcomes Trust. All Rights Reserved.  
 SF-36® is a registered trademark of Medical Outcomes Trust.  
 (SF-36v2 Standard, US Version 2.0)

**11. How TRUE or FALSE is each of the following statements for you?**

	Definitely true	Mostly true	Don't know	Mostly false	Definitely false
	▼	▼	▼	▼	▼
1. I seem to get sick a little easier than other people.....	 1	 2	 3	 4	 5
2. I am as healthy as anybody I know.....	 1	 2	 3	 4	 5
3. I expect my health to get worse .....	 1	 2	 3	 4	 5
4. My health is excellent.....	 1	 2	 3	 4	 5

***THANK YOU FOR COMPLETING THESE QUESTIONS!***

SF-36v2™ Health Survey © 1996, 2000 by QualityMetric Incorporated and Medical Outcomes Trust. All Rights Reserved.  
SF-36® is a registered trademark of Medical Outcomes Trust.  
(SF-36v2 Standard, US Version 2.0)

**APPENDIX F**  
**28-JOINT COUNT EXAMINATION FOR PAIN AND TENDERNESS**

(Sample provided in this appendix is for reference only.)

**28-Joint Count Examination for Pain and Tenderness**

ASSESSMENT OF JOINT TENDERNESS AND SWELLING AND JOINT COUNT

Upper Extremity	Joint Number	Right side			Left Side		
		Tenderness*	Swelling**	Not Assessed***	Tenderness*	Swelling**	Not Assessed***
Shoulder	1						
Elbow	2						
Wrist	3						
(includes radiocarpal, carpal, carpometacarpal considered as single unit)							
MCP I	4						
MCP II	5						
MCP III	6						
MCP IV	7						
MCP V	8						
IP	9						
PIP II	10						
PIP III	11						
PIP IV	12						
PIP V	13						
Lower Extremity							
Knee	14						
Joint Count							
*Tenderness Response 0 = Not Tender  1 = Positive response to questioning (tender), spontaneous response elicited (tender and winced) or withdrawal by subject on examination (tender, winced, and withdrew)		**Swelling Response 0 = None  1 = Detectable synovial thickening with or without loss of bony contours, or bulging synovial proliferation with or without cystic characteristics			***Not Assessed Do not score artificial or ankylosed joints; enter as NA  For missing joints enter NA		

**APPENDIX G**  
**FUNCTIONAL ASSESSMENT OF CHRONIC ILLNESS THERAPY–FATIGUE**

(Sample provided in this appendix is for reference only.)

**Functional Assessment of Chronic Illness Therapy–Fatigue FACIT-Fatigue  
 Scale (Version 4)**

Below is a list of statements that other people with your illness have said are important. **Please circle or mark one number per line to indicate your response as it applies to the past 7 days.**

		Not at all	A little bit	Some- what	Quite a bit	Very much
HI7	I feel fatigued	0	1	2	3	4
HI12	I feel weak all over	0	1	2	3	4
An1	I feel listless (“washed out”)	0	1	2	3	4
An2	I feel tired	0	1	2	3	4
An3	I have trouble starting things because I am tired	0	1	2	3	4
An4	I have trouble finishing things because I am tired	0	1	2	3	4
An5	I have energy	0	1	2	3	4
An7	I am able to do my usual activities	0	1	2	3	4
An8	I need to sleep during the day	0	1	2	3	4
An12	I am too tired to eat	0	1	2	3	4
An14	I need help doing my usual activities	0	1	2	3	4
An15	I am frustrated by being too tired to do the things I want to do	0	1	2	3	4
An16	I have to limit my social activity because I am tired	0	1	2	3	4

SOURCE: <http://www.facit.org/FACITOrg/Questionnaires>.

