### **3.11.2 Procedures Before Study Drug Treatment (Baseline/Start Study Drug Treatment [Visit 2/Week 0])**

Patients who meet the inclusion/exclusion criteria at visit 1 will continue to visit 2 (week 0); if they continue to meet all criteria, baseline evaluations will be conducted, randomization/stratification will occur via IRT, and study drug will be administered. NOTE: Week 0 refers to the start of the 1st week of study drug treatment, which will begin with the baseline visit.

In addition, a blood sample (5 mL) will be obtained for measurement of IPP-201101 plasma concentrations prior to and 5 minutes and 1, 2, and 24 hours after study drug administration from patients at selected North American and Western European study centers. The actual dates and times of study drug administration and the date and time of sampling will be recorded on the CRF.

The following procedures will be performed at visit 2:

- inclusion/exclusion criteria review
- physical examination symptom directed
- clinical laboratory tests
- ANA
- anti-dsDNA Ab, C3, and C4
- anti-U1-70K snRNP Ab, anti-Sm Ab, CRP, IgG, IgM, , IgA
- anti-IPP-201101 Ab
- vital signs measurements (includes systolic and diastolic blood pressures, pulse, and temperature)
- urine pregnancy test on all women regardless of childbearing potential
- concomitant medication review
- adverse event inquiry
- SLEDAI-2K
- BILAG-2004
- 28-joint count examination for pain and tenderness
- SFI
- SF-36
- PhGA
- FACIT-Fatigue
- C-SSRS Baseline version
- In vitro intracellular and secreted cytokine response
- access eCRF for randomization number and study drug administration. Randomization number and treatment number will be allocated automatically by the system.

A patient who is not enrolled in the study at the end of the baseline visit, eg, because entry

criteria were not met or enrollment did not occur within the specified time, may be considered for screening again if, eg, there was a change in the patient’s medical background or a modification of study entry criteria. (NOTE: Details of rescreening criteria and procedures are included in the Monitoring Plan for this study.)

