## **10.4 Data Handling Conventions**

All available data will be included for evaluation. For the purpose of efficacy analysis, missing or invalid values will be imputed using data from the previous visit for individual items and scores in the questionnaires and scales. For a derived score involving multiple items, the missing or invalid individual items will be imputed first before calculating the derived scores based on the complete individual item values. These rules apply only to the visits in which the patient is currently in the study and some data or an individual item is missing. If an assessment is not done at a visit, the missing data will not be imputed. The justification for using data from the previous visit is based on medical judgment. For the SF-36 questionnaire, the Half-Scale Missing Data Estimation (Half-Scale MDE) ([Ware et al 2007](#)) method will be used to estimate the missing values for calculating the 8 health domain scales.

Missing or invalid laboratory test results will not be estimated for biomarker analysis or safety analysis.

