  - anti-U1-70K snRNP Ab
  - anti-Sm Ab
  - CRP
  - IgG, IgM, IgA and IgE
- absolute and relative changes in the FACIT-Fatigue at weeks 12, 24, 36, and 52 (or final assessment)
- in vitro intracellular and secreted cytokine response

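### The previous-visit fill in Section 10.4 does not fit FACIT-Fatigue, which asks about 7 days and is given 12 to 16 weeks apart; the effect is small and on an exploratory endpoint only

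*Protocol*

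**What the plan says.** Protocol Section 10.4 sets one rule for efficacy instruments: "missing or invalid values will be imputed using data from the previous visit for individual items and scores in the questionnaires and scales". Items are filled first, and a multi-item score then comes from "calculating the derived scores based on the complete individual item values". The fill applies when the patient is still in the study and part of an assessment is missing. For a form not given at all, "If an assessment is not done at a visit, the missing data will not be imputed". The reason offered is: "The justification for using data from the previous visit is based on medical judgment".

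Only the SF-36 is taken out of this rule. Its eight domain scales use the half-scale method, which works within the form. FACIT-Fatigue is not mentioned, so the general rule covers it.

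Section 6.2.4 describes FACIT-Fatigue as a self-completed scale of 13 items. Its instruction in Appendix G reads: "Please circle or mark one number per line to indicate your response as it applies to the past 7 days". Table 2 and Section 3.11 place it at weeks 0, 12, 24, 36 and 52 (or early termination), the same visits as the SF-36. Sections 3.2.2 and 10.6.2 list its absolute and relative changes among the exploratory endpoints.

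**The concern.** Filling an item from the previous visit is reasonable for an index scored at every 4-weekly visit over a 4-week window, as SLEDAI-2K and BILAG-2004 are (Appendices C and D). It does not suit a 7-day questionnaire given about once a quarter. Either the previous visit holds no answer to carry, or the answer carried is months older than the period the form asks about. In both cases the rule ignores the other 12 answers given on the same day.

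At stake are the FACIT-Fatigue scores of patients who leave an item blank, above all at baseline, and a choice between two readings that give different scores and that the protocol leaves open.

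**Working it through.** **1. Rule against schedule.** Inputs: clinic visits at weeks 0, 2 and 4, then every 4 weeks to week 52 (Section 3.1), and the FACIT-Fatigue visits in Table 2.

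| FACIT form | Visit just before | FACIT at that visit? | Last earlier FACIT form | Age of its answers |
|---|---|---|---|---|
| Week 0 | Screening | No | None | – |
| Week 12 | Week 8 | No | Week 0 | 12 weeks |
| Week 24 | Week 20 | No | Week 12 | 12 weeks |
| Week 36 | Week 32 | No | Week 24 | 12 weeks |
| Week 52 | Week 48 | No | Week 36 | 16 weeks |

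The procedure lists in Sections 3.11.1, 3.11.3.3, 3.11.3.5, 3.11.3.7 and 3.11.3.9 agree with Table 2. An early-termination form can fall 4 or 8 weeks after the last one. At weeks 16, 28 and 40 the previous visit does hold a FACIT form, but its answers are still about 4 weeks old against a 7-day recall.

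**2. Last-form reading, week 12.** The inserted answer is the baseline answer, so that item's change is zero. If change is even across items, a patient with one filled item loses 1/13 = 7.7% of the change. Averaged over patients, with each item blank at rate b independently of its change, expected change is (1 − b) times the full change. The shrinkage is therefore b itself: 0.5%, 1% or 2% for b = 0.5%, 1% or 2%. If b is equal in both arms, the treatment difference shrinks by the same fraction. At later visits only the change since the last form is lost for that item.

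**3. Blank at baseline.** No earlier form exists, so no complete-item baseline score can be formed, and no change score at any visit. With 13 items blank independently at rate b, the share of forms with at least one blank is 1 − (1 − b)^13:

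- b = 0.5%: 6.3%
- b = 1%: 12.2%
- b = 2%: 23.1%

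The protocol gives no blank rate; these values of b are assumptions. Clustering of blanks within patients would lower the shares.

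**4. Carry-forward against a same-form mean.** Assume equal item means and variances, inter-item correlation ρ and 12-week correlation r of the same item. In units of one item's variance, the error variance is:

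- carry-forward: 2(1 − r); at r = 0.5 this is 1.0
- mean of the other 12 items: 1 + (1/12 + 11ρ/12) − 2ρ; at ρ = 0.6 this is 1 + 0.633 − 1.2 = 0.433

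Over ρ from 0.5 to 0.7 and r from 0.4 to 0.6, the ratio of the second to the first runs from 0.27 to 0.68. On the 13-item total the gain is slight. At ρ = 0.6 the total has variance 13 + 156 × 0.6 = 106.6, so one filled item adds 1.0/106.6 = 0.9% against 0.433/106.6 = 0.4%, and only on affected forms.

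**The case against.** The strongest reply is that Section 10.4 says missing items will be imputed and never says that a score is dropped. The literal reading makes the rule unusable at all four scheduled post-baseline forms, which is a reason to doubt that it was meant. On the workable reading, the last form holding the item, the loss is 2% of mean change or less at the assumed rates. FACIT-Fatigue is exploratory with no test or power attached, Section 10.6.3.2 plans only descriptive summaries even for secondary variables, and instrument scoring is often left to the statistical analysis plan.

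The same-form mean also has a weakness. Items such as feeling tired and being too tired to eat probably differ in average level, so a mean of the others can be biased for one of them. Carrying the same item forward does not have that bias.

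Most of this stands as a limit on size. It does not rescue the rule. Section 10.4 states a rule for all questionnaires and scales, so a different FACIT rule in the analysis plan would depart from the protocol. A baseline blank fails on either reading. The SF-36, collected at the same visits, already has a within-form rule.

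**Conclusion.** Section 10.4 fixes a rule that FACIT-Fatigue's schedule and recall period do not support. At scheduled post-baseline forms, a blank either cannot be filled or is filled with an answer 12 weeks old (16 at week 52). At baseline it cannot be filled at all. The point is minor: the endpoint is exploratory and the primary SRI analysis is untouched. The sizes are about 0.5% to 2% shrinkage of mean change at week 12 on the last-form reading, and about 6% to 23% of baseline forms with a blank. Both rest on assumed item-blank rates of 0.5% to 2%, and the second also on independence.

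A reader might infer more: that blanks are frequent, or that 1 − (1 − b)^26 = 12%, 23% or 41% of baseline-plus-visit pairs would be lost. The documents support neither. They report no blank rate, and loss of a post-baseline score is only an inference from the complete-item wording combined with the literal reading of the previous visit. The mismatch between rule and schedule does not depend on any of these rates.

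**What to change.** In Section 10.4, add a FACIT-Fatigue rule of the kind already given to the SF-36:

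- If at least 7 of the 13 items are answered (half is 6.5), replace each blank with the patient's mean of the answered items on that form, baseline included.
- Align item direction first: An5 and An7 are positively worded, unlike the other 11.
- With fewer than 7 answered, treat the score as missing.
- Do not carry items from an earlier form.

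This costs one or two sentences, no new data and no change to the sample size. It should be fixed before unblinding, so that the choice between readings is not made with results in view. The price is a possible slight bias where items differ in average level.
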